6.5. STATISTICAL TESTS

The default significance level will be 0.05, confidence intervals will be 95%, and all tests will be 2-sided, unless otherwise specified in the description of the analyses.

6.6. COMMON CALCULATIONS

For quantitative measurements, change from baseline and proportions will be calculated as:

- Change from Baseline = Test Value at Visit X – Baseline Value

- Percent Change from Baseline = $((\text{Test Value at Visit X} - \text{Baseline Value}) / \text{Baseline Value}) * 100$
- Proportion at Visit X = Number of subjects satisfying criteria at Visit X / Total number of subjects at Visit X

6.7. GENERAL STUDY INFORMATION

A general table with summary of study information will be generated, including date of first subject signed informed consent form (ICF), last subject visit date and database lock date. All analyses will be conducted using SAS® (version 9.4, SAS Institute Inc., Cary, NC).

CCI

[REDACTED]

8. STATISTICAL CONSIDERATIONS

8.1. ADJUSTMENTS FOR COVARIATES AND FACTORS TO BE INCLUDED IN ANALYSES

The following covariates and factors, and/or endpoint Baseline measure are used in the analyses. For details of their inclusion in the models, see the specific analysis section.

- Baseline history of esophageal dilation (Yes/No)
- Concurrent PPI therapy (Yes/No)

If a subject was assigned the wrong stratum at randomization, their reported stratum based on the randomization system will be used for the statistical analyses. Analyses may be repeated using actual stratum based on eCRF as sensitivity analysis if randomization based on mis-stratification occurs in more than 10% of randomized subjects.

8.2. MULTICENTER STUDIES

- This study will be conducted by multiple investigators at multiple centers internationally.

Data from all sites will be pooled and statistical analyses will not be adjusted for investigational site, country, or geographic region.

8.3. MISSING DATA

Missing adverse event (AE) relationship to study drug and AE seriousness will be imputed as described in Section 17.1.1.2 and 17.1.3, respectively. Partial or missing AE start dates, Concomitant Medication (CM) start dates, and hospitalization dates will also be imputed as described in Appendix 2. No other missing safety data will be imputed.

Missing efficacy data will be handled as described in Sections 16.1.2, 16.2.2, and 16.3.2. In the primary analysis of the primary endpoint, PEC after rescue medication and/or rescue procedure uses will be set to missing; all missing data will then be imputed in the FAS using multiple imputation. In the main analyses of all binary responder-type endpoints, all subjects with missing data, regardless of reason for missingness, will be considered as nonresponders. In the main analysis of continuous or score endpoints, subjects with missing data will be handled using observed cases only, multiple imputation, or a linear mixed effect model.

8.4. MULTIPLE COMPARISONS/ MULTIPLICITY

For Double Blinded Treatment Period, hypotheses tests will be performed for efficacy endpoints for the comparison of etrasimod dose versus the placebo group. However, these hypothesis tests will not be controlled for type-I error rate. Un-adjusted p-values will be reported. The associated 95% confidence intervals will be reported.

For the Extension Treatment Period, no hypothesis tests between treatment groups will be performed; only descriptive statistics will be provided.

8.5. SUBGROUP ANALYSES

The following subgroups will be assessed for the primary, secondary, and CCI endpoints:

- Sex (Female, Male)
- Race (white, non-white)
- Age (\leq Median, $>$ Median)
- History of Dilation (Yes, No)
- Duration of Disease (\leq Median, $>$ Median)
- Concurrent PPI Therapy (Yes, No)
- Concurrent Atopic Comorbidities (Yes, No)

- Concurrent Elimination Diet (Yes, No)
- Baseline Esophageal PEC (\leq Median, $>$ Median)
- Baseline DSQ Score (\leq Median, $>$ Median)
- Baseline Eosinophilic Esophagitis Endoscopic Reference Score (EREFS) (\leq Median, $>$ Median)
- Baseline Swallowed Topical Steroid Treatment Refractory Status (Yes, No)

Additional subgroups may be assessed, if deemed necessary. The medians will be derived based on the FAS for all subgroups cut at the median. It should be noted that the study was not designed to detect treatment differences with high statistical power within subgroups. If any subgroup includes $<$ 5% of all subjects, no inferential statistics will be generated.

The actual stratum at Baseline will be used for all subgroup analyses.

9. OUTPUT PRESENTATIONS

0 shows conventions for presentation of data in outputs.

10. DISPOSITION AND PROTOCOL DEVIATIONS

All subjects who provide informed consent will be accounted for in this study. Inclusion criteria not met and exclusion criteria met will be listed.

Among the randomized subjects, the number and percent of subjects who completed/discontinued treatment, reasons off treatment, the number and percent of subjects who completed/discontinued the study, and reasons off study will be summarized in all randomized subjects. This summary will also be provided by region and country. The number and percent of subjects in each analysis set will be summarized in all randomized subjects. An additional summary of the number of subjects screened, the number of screen failed subjects, and reason for screen failure will be presented for all screened subjects. A listing of subjects whose blind was broken will be provided. The number of subjects whose visit was impacted by the COVID-19 pandemic per CRF will also be summarized by nominal visit.

During site monitoring, protocol deviations will be graded as Critical, Major, or Minor. According to ICH E3 and ICH E3(R1), important protocol deviations are a subset of protocol deviations that might significantly affect the completeness, accuracy, and/or reliability of the study data or that might significantly affect a subject's rights, safety, or well-being (ICH 1995, ICH 2012). For example, important protocol deviations might include enrolling subjects in violation of key eligibility criteria designed to ensure a specific subject population or failing to collect data necessary to interpret primary endpoints, as this may compromise the scientific value of the study.

During the review of all reported deviations, important deviations related to study inclusion or exclusion criteria, conduct of the study, patient management, or patient assessment will be identified. Where relevant the importance of a potentially important protocol deviations will be assessed in the context of the study's estimands to evaluate potential impact. All important protocol deviations will be summarized for the FAS in the following categories in descending frequency by study treatment group.

All protocol deviations will be listed, including whether a deviation was impacted by the COVID-19 pandemic (Yes or No). Protocol deviation categories include but are not limited to the following:

- Informed Consent and Process
- Inclusion Criteria
- Exclusion Criteria
- Concomitant Medication Criteria
- Laboratory Assessment Criteria
- Study Procedures Criteria
- Blinding
- Patient Report Outcomes
- Safety
- Visit Schedule criteria
- Investigational Product Condition
- Subject Investigational Product Compliance
- Investigation Product (IP) Administration
- Efficacy Criteria
- Source Document Criteria
- Subject Discontinuation

Note, all protocol deviation categories above are based on the final PDMP that is completed after May 2022 except for Source Document Criteria, which is based on old PDMP prior to May 2022.

Important protocol deviations will also be summarized by whether they were impacted by COVID-19 pandemic (Yes or No). Additionally, a summary of missing endoscopy regardless of reason and missing endoscopy due to visit impacted by the COVID-19 pandemic will be presented by visit. The summary of important protocol deviations will be provided for Double-blinded Treatment period and Extension Treatment period, respectively.

The protocol deviation categories above are based on the latest version of PDMP and associated protocol deviation

categories prior to the unblinding of Double-blind Treatment period. If there is any update for these 2 documents regarding the protocol deviation categories after the unblinding of Double-blind Treatment period, the summary and listings regarding protocol deviation could be subject to be updated if deemed needed.

11. DEMOGRAPHIC AND OTHER BASELINE CHARACTERISTICS

The following demographic data and Baseline characteristics will be summarized for the FAS:

- Age on consent (years)
- Sex
- Race
- Ethnicity
- Woman of childbearing potential (Yes or No)
- Height (cm)
- Weight (kg)
- Body mass index (BMI) (kg/m^2)
- Alcohol consumption (Yes or No)
- Tobacco use (Yes or No)
- This summary will be repeated for age, sex, race, ethnicity, or woman of childbearing potential for subjects who fail screening.

The following Baseline characteristics related to EoE will be summarized for the FAS:

- Primary EoE Symptom experienced (Dysphagia, Food Impaction, Specific food avoidance, other)
- Duration of EoE (years)
- History of Esophageal Dilation (Yes or No)
 - Subjects with more than 1 esophageal dilation (Yes or No)
 - Duration of Time Between the Last 2 Esophageal dilation procedures (months)
 - Impact of Dilation on EoE symptoms
 - Complications Related to Dilation Procedure (Yes or No)
- EoE Histopathologic Phenotype
- Biopsy of the esophagus previously assessed for PEC (Yes or No)
- Esophageal Level assessed for PEC: Proximal, Mild, Distal
- Endoscopic Findings
- Comorbid Conditions
- Type of Dietary Therapy
- Food Groups Eliminated from Food Elimination Diet
- Reason for Discontinuation of Diet

- Family History of EoE (Yes or No)
 - Relation
 - Type
- Baseline history of esophageal dilation (Yes or No) – Reported (used for stratification at randomization)
- Baseline history of esophageal dilation (Yes or No) – Actual (reported on the eCRF)
- Baseline history of esophageal dilation – Difference
- Concurrent PPI therapy (Yes or No) – Reported (used for stratification at randomization)
- Concurrent PPI therapy (Yes or No) – Actual (reported on the eCRF). The reference start date used to identify the Concurrent PPI therapy status is the date of randomization
- Concurrent PPI therapy – Difference
- Baseline PEC (eos/hpf)
- Prior EoE Treatment (Yes or No)
- Reason for Prior EoE Treatment Discontinuation

- Prior treatment for EoE will be summarized, including category of treatment, reason for discontinuation, and estimated duration (weeks) of treatment over the last 12 months.

12. DERIVATIONS

- Duration of EoE (years) = (Informed consent date – Date of diagnosis + 1) / 365.25
- Weight (kg) = Weight (lb) × 0.4536
- Height (cm) = Height (in) × 2.54
- Height (m) = Height (in) × 0.0254 = Height (cm) × 0.01
- BMI (kg/m²) = Weight (kg) / Height (m)²

13. MEDICAL HISTORY

Medical history will be collected on the medical history eCRF and coded using Medical Dictionary for Regulatory Activities (MedDRA, version 25.1 or higher). The version used to code medical history will be displayed in the outputs. All medical history will be summarized for the Safety Set by system organ class (SOC) and preferred term (PT).

14. MEDICATIONS

Medications will be captured on the Concomitant Medications eCRF and coded using the WHO Drug dictionary (WHODD01SEP2021 or later version). Refer to APPENDIX 2 for handling of partial dates for medications. In the case where it is not possible to define a medication as prior or concomitant, the medication will be classified by the worst case (i.e. concomitant).

- ‘Prior’ medications are medications which started and stopped prior to the first dose of study treatment.
- ‘Concomitant’ medications for the Double-Blind Treatment Period are medications which started prior to, on or after the first dose of study treatment AND ended on or after the date of first dose of study treatment or were ongoing at the end of the study.
- ‘Concomitant’ medications for the Extension Period are medications which started prior to, on or after the first dose of study treatment in the Extension Period AND ended on or after the date of first dose of study treatment in the Extension Period or were ongoing.

Concomitant medications will be summarized by Anatomical-Therapeutic-Chemical (ATC) Level 2 and Preferred Drug name for the Safety Set. Concomitant medications used for ongoing EoE will be flagged as such on the Concomitant Medications eCRF and summarized by ATC Level 2 and Preferred Drug name for the Safety Set. Concomitant medication summaries will be prepared for the End of Double-Blind Treatment Period and End of Extension Period, respectively.

Prior therapies for EoE, which will be captured on EoE Prior Therapies eCRF, will also be summarized by ATC Level 2 and Preferred Drug name for the Safety Set.

15. STUDY MEDICATION EXPOSURE

Exposure to study treatment in weeks will be summarized for the Safety Set for the End of Double-Blind Period, Extension Period, and overall, respectively. For overall exposure to study treatment in the Double-Blind Treatment Period, the date of first and last study treatment administration will be taken from the Dosing Administration for Double-Blind Period eCRF. For the overall exposure to study treatment in the Extension Period, the date of first and last study treatment will be taken from the Dosing Administration for Extension Period eCRF. Exposure for the entire study may also be summarized, in which case, the earliest study treatment date from both periods will be used for the first date and the latest study treatment date in both periods will be used for the last date. Interruptions, compliance, and dose changes are not taken into account for duration of exposure. Total subject-years on study will also be summarized.

Dose interruptions will be recorded on the Dosing Administration for Double-Blind Period and Dosing Administration for Extension Period eCRFs. Overdoses will be recorded on the Overdose eCRF. The frequency and percentage of subjects who had at least one dose interruption, who had at least one dose interruption of >7 days, who

had at least one dose interruption of >14 days, who had one overdose, and who had >1 overdose will be summarized for the Safety Set.

15.1. DERIVATIONS

Duration of exposure (weeks) = (date of last study treatment administration – date of first study treatment administration + 1) / 7. For subjects with missing study treatment end dates collected on the Dosing Administration eCRFs, their date of last study treatment administration will be imputed by the last date of all dosing administration start/stop dates recorded.

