7.4. Accountability

Subjects will be instructed to record tablet self-administration daily and to document the time of their last dose prior to each study visit in an electronic diary (eDiary) that will be reviewed at each study visit by study site staff.

At each site visit, subjects will return all dispensed medication bottles and any remaining tablets to study site staff; remaining tablets will be collected and counted by the Investigator or qualified staff to confirm subject compliance. The number of remaining tablets in the bottle may be counted by visual inspection via videoconferencing for virtual assessment. In this scenario, all bottles and any remaining tablets must be returned at the next study site visit.

The Investigator must maintain adequate records documenting the receipt, use, loss, or other disposition of study treatment tablets. To ensure adequate records, all drug supplies will be accounted for in the drug accountability inventory and will be monitored by counting of unused study treatment tablets.

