10.5. Pharmacokinetic Assessments

Blood samples for plasma analysis of etrasimod will be collected at the following timepoints from all subjects who received ≥ 1 dose of study drug (etrasimod or placebo):

- Predose and at 4 hours (± 15 minutes) postdose (after ECG) on Day 1
- Predose (trough; within 60 minutes prior to dosing) at Weeks 4, 8, 16, 24, 28, 32, 46, and 52 or at the ET Visit, if applicable

- At the 4-Week Safety Follow-Up Visit (28 days [\pm 3 days] after the last dose of study drug)
- If possible, at the time of an AE leading to study drug discontinuation or when there is a significant AE such as a severe or atypical infection (including but not limited to systemic infections like sepsis) and severe drug induced liver injury that meets Hy's criteria [49]. The time of the last study treatment dose should be documented.

Subjects should be instructed to document the time of their last dose prior to the study visit (Section 7.4) and the time must be recorded in the eCRF. The time of PK sample obtained pre-dose and when study drug is administered during the study visit must also be recorded in the source.

Blood samples will be processed for collection of plasma fractions for determination of the concentrations of etrasimod and, if warranted, metabolites of interest. Blood samples collected for PK analyses may also be used for profiling of drug-binding proteins, bioanalytical method validation purposes, stability assessments, metabolite assessments, or to assess other actions of etrasimod with plasma constituents.

No urine samples will be collected for PK analysis.

Drug concentration information that would unblind the study will not be reported to investigative sites or blinded personnel until the study has been unblinded.

Planned timepoints for all PK assessments are provided in the Schedules of Assessments (Appendix 1; Table 7 and Table 8).

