16.1. DERIVATIONS

Compliance to study treatment is based on the Drug Accountability eCRF and will be calculated as the number of tablets taken (total dispensed – total returned) divided by the prescribed number of tablets expected during the treatment period, expressed as a percentage, see calculations below.

The total number of tablets expected is defined as the number of tablets that a subject is expected to have taken between their first and last study treatment administration and is numerically identical to the subject's overall study treatment exposure, since the medication is to be taken once daily. On any site visit day, the medication is to be held and taken at the site, after all predose assessments have been completed. For example, if a subject took their last dose of study treatment on Day 60 and returned to the site on Day 78 to return the study treatment bottle, then the total number of tablets expected would be 60, not 77.

- Overall Compliance to study treatment will be calculated as follows:

$$\frac{([\text{Total N of tablets dispensed in the study}] - [\text{Total N of tablets returned in the study}])}{[\text{Date of last dose}] - [\text{Date of first dose}] + 1} \times 100$$

If a bottle is not returned, all dispensed tablets will be assumed to be taken. For each subject, if a high percentage (> 25%) of bottles were not returned by a subject, additional analyses may be done where bottles not returned are excluded from the overall compliance calculation for the subject. In such analysis, the date of last dose or the date of last bottle return, whichever is earlier, will be used as the “date of last dose” in the calculation above.

Both scheduled and unscheduled study treatment dispensations will be used in the compliance calculation. Overall

compliance calculations will be performed for the Double-Blind Treatment Period and the entire study and will be used in determining inclusion/exclusion of subjects in the Per Protocol Set. For subjects discontinued prior to Week 16, their overall compliance for the 16 Week Treatment Period and the entire study will be identical. For subjects who remained in the study beyond Week 16, the 16 Week total tablets expected will be defined as Date of Week 16 visit – Date of first dose, since their last dose in the 16 Week Treatment Period should have been taken on the day before Week 16 visit.

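### A missing last-dose date is imputed from dosing-form dates alone, so exposure can collapse to the start or restart date although later doses are documented elsewhere

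*SAP*

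**What the plan says.** SAP Section 15.1 defines exposure by "Duration of exposure (weeks) = (date of last study treatment administration – date of first study treatment administration + 1) / 7". When the end date is missing from the Dosing Administration forms, "their date of last study treatment administration will be imputed by the last date of all dosing administration start/stop dates recorded". It gives no second source and no upper limit.

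SAP Section 15 takes first and last administration dates from those forms and adds that "Dose interruptions will be recorded on the Dosing Administration for Double-Blind Period and Dosing Administration for Extension Period eCRFs". It also states that "Interruptions, compliance, and dose changes are not taken into account for duration of exposure". Interruptions are the only thing the SAP names that would put further dates on the form.

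SAP Section 16.1 carries the result into compliance. The expected tablets are those due "between their first and last study treatment administration and is numerically identical to" the subject's exposure. Tablets in a bottle that is not returned count as taken.

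The protocol requires later intake to be documented elsewhere. Section 7.4: "Subjects will be instructed to record tablet self-administration daily and to document the time of their last dose prior to each study visit", in the eDiary. Section 10.5 says of that last-dose time at PK visits that "the time must be recorded in the eCRF". Appendix 1, Table 7, schedules in-person dosing on Day 1 and at Weeks 4, 8, 16 and 24.

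**The concern.** The rule is needed mainly for subjects who stop without a recorded end date. If their course is an open record, the latest date on the form says when that stretch of dosing began, not when it ended. The whole final stretch is then lost, although the trial holds evidence of later doses.

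At stake are the descriptive summary of weeks of exposure and the compliance table, which uses the same dates in its denominator. There is a possible knock-on. SAP Appendix 4 does not count rescue therapy in the follow-up period, which it describes as beginning on or after the date of last study treatment administration. It does not say whether an imputed date may serve.

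**Working it through.** **Inputs.** Exposure formula and imputation rule: SAP 15.1. Visit days 29, 57 and 113 for Weeks 4, 8 and 16: Protocol Table 7. Planned N of 96 at 3:3:2, so 96 × 3/8 = 36 per etrasimod arm: Protocol synopsis. Assumption: one start/stop record per uninterrupted stretch of dosing.

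**The plan's own figure.** The example in SAP 16.1 has the last dose on Day 60 and the bottle returned on Day 78. Expected tablets = 60 − 1 + 1 = 60, as stated; the rejected figure is 78 − 1 = 77. So the SAP means the denominator to follow the actual last dose.

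**No interruption, stop date blank.** The only date on the form is Day 1. Exposure = 1 − 1 + 1 = 1 day; 1/7 = 0.14 weeks. Compare the latest documented dose:

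| Last documented dose | Exposure from that dose | Exposure under the rule |
|---|---|---|
| Week 4, Day 29 | 29 days, 4.14 weeks | 1 day, 0.14 weeks |
| Week 8, Day 57 | 57 days, 8.14 weeks | 1 day, 0.14 weeks |
| Week 16, Day 113 | 113 days, 16.14 weeks | 1 day, 0.14 weeks |

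**One interruption.** With a restart on Day 25 (an illustration) and no later stop date, exposure is 25 days = 3.57 weeks, however long dosing continued.

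**One row per visit instead.** The latest row is then the last recorded visit, and the loss is only the time from that row to the true last dose.

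**Effect on an arm mean.** Shift = k × (last documented day − 1) / 7 / 36, where the number of subjects k is assumed:
- k = 1, Week 8: 8/36 = 0.22 weeks
- k = 4, Week 8: 32/36 = 0.89 weeks
- k = 4, Week 16: 64/36 = 1.78 weeks

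**Compliance.** Table 7 dispenses drug on Day 1 and at Week 8. Assume 8-week supplies (the size is not stated). A subject seen at Week 8 and then lost has about 56 tablets used before that visit plus 56 in an unreturned bottle that count as taken: 112. Under the rule, 112/1 = 11,200%. With Day 57 as last dose, 112/57 = 196%. The better date removes the absurd figure, but the subject still exceeds 120% because of the unreturned-bottle rule.

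**Appendix 4.** Suppose rescue starts between the first dose and Week 16, a Week 16 biopsy is taken, and the stop date stays blank. If the imputed Day 1 is used, that rescue falls after the supposed last dose and is not counted. The post-rescue eosinophil count would then stay in the analysis, whereas SAP 17.1.2 would set it to missing. If the latest documented dose follows the start of rescue, using that date keeps the rescue in.

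**The case against.** The strongest objection is that the form is not in the documents. The rule refers to all recorded start/stop dates, and SAP Section 16 bases tablet counts on Dosing Administration in the EDC, which would fit a form with more rows than one open interval. This stands: the one-day result is conditional and cannot be stated as fact.

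The trigger should also be uncommon. Queries are to be resolved before each analysis (SAP 4.1, 4.2). Investigators should try to document the last intake when consent is withdrawn (Protocol 8.2), and early-termination visits are due within 7 days of the last dose (Protocol 9.6). The documents give no expected number of missing end dates, so the subject counts used above are only illustrative.

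A reader might infer wider damage. The documents do not support it:
- **Subject-years.** SAP Section 15 and Protocol 11.9.3 summarize subject-years on study, not on treatment.
- **Exposure-adjusted rates.** For adverse events of special interest, SAP 18.2.6 counts time to first event or last participation, not last dose.
- **Per Protocol Set.** A subject lost before Week 16 normally has no Week 16 eosinophil count and is already excluded under SAP 5.5. For subjects who stay beyond Week 16, the 16-week denominator in SAP 16.1 uses the visit date. A little ambiguity remains, because SAP 16.1 also says that compliance over the double-blind period and the entire study informs the set.
- **Open extension records at the Main Analysis.** That analysis is for the end of the double-blind period, whose dates come from a separate form. Nothing says that extension exposure is tabulated then.

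On Appendix 4, the rescue list is settled by blinded clinical review, which may catch an implausible date. But the text leaves the choice of date open.

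**Conclusion.** The point holds as a defect in a fallback rule. SAP 15.1 draws on one form, ignores better evidence the trial collects, and can return the start or restart date as the last dose. Under the single-record assumption, exposure is 0.14 weeks against 4.14, 8.14 or 16.14 weeks documented; under a row-per-visit layout the loss is only the time since the last row. The reach is the weeks-of-exposure summary and the compliance denominator, plus rescue identification if Appendix 4 uses the imputed date. It would be wrong to conclude that every subject lost to follow-up is credited with one day, or that safety rates are distorted. This is a low-priority correction, worth making because it is simple.

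**What to change.** Replace the sentence in SAP 15.1 so that a missing last-dose date is imputed as the latest documented intake among:
- the Dosing Administration dates;
- the eDiary tablet entries;
- the last-dose date/time in the eCRF at PK visits;
- in-person dosing.

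Cap the date at study discontinuation. Use the same date in the SAP 16.1 denominator, and state in Appendix 4 which last-administration date it uses.

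The cost is SAP wording and a little programming to combine sources; no new data collection is required by the protocol. One check is needed: Protocol 10.5 asks for the time of on-site dosing in the source, and only the last dose before the visit is expressly required in the eCRF. If on-site doses are not in the database, the pre-visit dose and the eDiary can serve. For a subject dosing daily and last seen on Day 57, relying on the pre-visit dose alone would cost one day (56 rather than 57).
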